**Table 2 Data Collection per Visit**

Case Report Form	Eligibility/ Baseline Visit	Return Visits	Retrospective Visits (optional)	Final Visit c
Written informed consent/assent	X	--	--	--
Inclusion/exclusion criteria	X	--	--	--

PFIZER CONFIDENTIAL

Case Report Form	Eligibility/ Baseline Visit	Return Visits	Retrospective Visits (optional)	Final Visit c
Patient demographics date of birth, gender, ethnic origin	X	--	--	--
Clinical trial and compassionate use program participation (log format)	X	X	X	
TTR data genetic test results, tissue biopsy	X	--	--	--
Family history of ATTR amyloidosis	X	--	--	--
Medical history past and current signs, symptoms and medical diagnoses	X	--	--	--
Annual updated medical assessment current signs and symptoms	--	X	--	X
General exam weight/height, vital signs, CCI [REDACTED]	X	X	X	X
Concomitant medications (log format) category, indication, start and stop dates	X	X	X	X
Tafamidis treatments (log format) dose, start and stop dates	X	X	X	
Hospitalizations (log format) admission and discharge dates, reason for hospitalization	--	X	X	X
Transplant history and complications (log format) date(s) of transplant(s), organ(s) transplanted, information on complications	X	X	X	X
Adverse events	X	X	X	X
Laboratory data Hematology, clinical chemistry, urinalysis, including glomerular filtration rate [GFR]	X	X	X	X
CCI [REDACTED]	■	■	■	■
[REDACTED]	■	■	■	■
Nerve conduction studies: Upper Extremity, Lower Extremity				
Renal/bladder ultrasound a residual volume, number and size of kidneys, echogenicity	X	X	X	X

Case Report Form	Eligibility/ Baseline Visit	Return Visits	Retrospective Visits (optional)	Final Visit c
Eye examination a intraocular pressure, vitreous, presence of opacities	X	X	X	X
Body composition a total bone mineral density and content, total lean and fat mass	X	X	X	X
CCI [REDACTED]	■	■		X
Patient death b			X	
Patient discontinuation b			X	
Patient status update b			X	

a Printed assessment worksheets will be available to provide to outside specialists performing assessment(s).

b Data on patient deaths, discontinuations, and status assessments will be collected independent of the visit schedule.

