### Predominantly Cardiac Phenotype

Predominantly cardiac phenotype includes:

1) Wild type ATTR-CM patients (symptomatic or not) with or without neurologic or gastrointestinal symptoms as follow:

- Neurologic or gastrointestinal (GI) symptoms (erectile dysfunction, constipation, and carpal tunnel) of any severity related or not to ATTR; OR
- Neurologic or gastrointestinal (GI) symptoms (other than erectile dysfunction, constipation, and carpal tunnel) of any severity if unrelated to ATTR; OR
- Neurologic or gastrointestinal (GI) symptoms (other than erectile dysfunction, constipation, and carpal tunnel) of mild severity if related or possibly related to ATTR; AND

- CCI [REDACTED]  
[REDACTED]

Cardiac and neurologic symptoms do not need to be ongoing at a given visit to be included for phenotyping.

2) Symptomatic ATTRv amyloidosis participants that fulfil the following criteria:

- Presence of abnormal electrocardiogram (ECG) due to rhythm disturbance, heart failure, or dyspnea) of any severity; AND
- Absence of neurologic or gastrointestinal (GI) symptoms (ATTR unrelated, related or possibly symptoms) reported in medical history; AND
- CCI [REDACTED]  
[REDACTED]

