## 2) Symptomatic ATTRv amyloidosis participants that fulfil the following criteria:

- Abnormal ECG due to rhythm disturbance, heart failure, or dyspnea, AND
- Any ongoing neurologic or GI symptoms including erectile dysfunction, constipation, carpal tunnel syndrome of any severity, AND / OR
- A mPND score  $\geq$  I

Mixed phenotype will not be combined with any other phenotype when analyzing the data.

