**Unclassified Phenotype**

Participants who do not qualify as predominately cardiac, neurologic, mixed phenotype or are asymptomatic.

Additional details about the phenotypes can be found in Table 3 below.

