**Table 3: Phenotype classification**

Phenotype	Genotype	Symptomatic	Cardiac symptoms with medical history="cardiovascular"	Cardiac symptoms ongoing status	Cardiac symptom severity	Neurologic symptoms with medical history="Neurologic" or "GI"	Neurologic symptoms ongoing status	Neurologic symptoms severity	mPNDscore
Predominantly cardiac	ATTRwt	Yes/ No	Rhythm disturbance/Heart failure/Dyspnoea	Either ongoing or not ongoing	Any severity	Erectile dysfunction/constipation/carpal tunnel syndrome	Ongoing/or not	Any severity related or not	< 1 or missing
	ATTRwt	Yes/ No	Rhythm disturbance/Heart failure/Dyspnoea	Either ongoing or not ongoing	Any severity	Any neuro/GI symptoms other than Erectile dysfunction/constipation/carpal tunnel syndrome	Ongoing /or not	Any severity if unrelated, or Mild related, possibly related	< 1 or missing
	ATTRv	Yes	Rhythm disturbance/Heart failure/Dyspnoea	Either ongoing or not ongoing	Any severity	No neuro or GI TTR related or possibly symptoms	none	none	< 1 or missing
Predominantly neurologic	ATTRv	Yes	Any cardiac symptoms except Rhythm disturbance/Heart failure/Dyspnoea or No cardiac symptoms	Either ongoing or not ongoing	Any severity	Any neuro/GI symptoms including Erectile dysfunction/constipation/carpal tunnel syndrome	Ongoing	Any	1 or Missing
	ATTRv	Yes	Any cardiac symptoms except Rhythm disturbance/Heart failure/Dyspnoea or No cardiac symptoms	Either ongoing or not ongoing	Any severity	Missing	Missing	Missing	1

Mixed	ATTRwt	Yes	Rhythm disturbance/Heart failure/Dyspnoea	Either ongoing or not ongoing	Any severity	Any neuro/GI symptoms excluding Erectile dysfunction/constipation/carpal tunnel syndrome	Ongoing	Moderate/Severe related or possibility related	1 or missing with symptoms as described
	ATTRv	Yes	Rhythm disturbance/Heart failure/Dyspnoea	Either ongoing or not ongoing	Any severity	Any neuro/GI symptoms including Erectile dysfunction/constipation/carpal tunnel syndrome	Ongoing	Any	1 or missing (if missing must have symptoms as described)

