**The other subgroups to be considered are as follows:**

- CCI [REDACTED]
- Severe hepatic impairment (only to be used corresponding to tafamidis treated set). The patients with severe hepatic impairment at baseline will be identified by any of the following:
  - The following pre-coded terms on the Gastrointestinal medical history and the Gastrointestinal general assessment forms: Hepatitis, Cirrhosis, Gastrointestinal malignancy, Hepatotoxicity, Other hepatic impairment having severity scale as “severe”.
  - The following terms appearing in the database as entered on the Other Gastrointestinal Medical History or General Assessment forms at baseline and assessed as ‘severe’: “severe impaired hepatic function”, “severe hepatic dysfunction”, “severe liver dysfunction/liver failure”. Other similar terms as identified during the final database lock of this study may be investigated to identify patients with severe hepatic impairment at baseline.
- Patients not on tafamidis at the time of enrollment on THAOS who had a liver transplant prior to enrollment on THAOS
- Patients not on tafamidis at the time of enrollment on THAOS who had a liver transplant after enrollment on THAOS
- Patients not on tafamidis at the time of enrollment on THAOS without any liver transplant either before or after enrollment on THAOS
- Patients treated with tafamidis at any time in THAOS and with a liver transplant prior to first dose of tafamidis
- Patients treated with tafamidis at any time in THAOS and with a liver transplant after the first dose of tafamidis
- Patients treated with tafamidis at any time in THAOS and never had a liver transplant
- Off-label use of 80/61 milligram (mg) of tafamidis (only to be used corresponding to tafamidis treated set) defined as:
  - Patients not classified as predominantly cardiac or mixed phenotype at the first date of dosing with a dose of 80/61 milligram (mg) of tafamidis.
- Predominantly neurologic at baseline who become mixed phenotype post baseline\*
- Predominantly cardiac at baseline who become mixed phenotype post baseline\*

Sample size in a subgroup needs to be at least 10 in order to have sufficient data to provide descriptive statistics, listings will be provided for smaller subgroups.

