**\*Changes of phenotype**

Under the assumption that phenotype-related symptoms do not truly disappear, but are only possibly masked or temporarily resolved, once determined, phenotype classification

PFIZER CONFIDENTIAL

will be carried forward to future visits even if there are no available symptom data at the subsequent visit. Patients classified as predominantly cardiac or predominantly neurologic at a given visit will continue to be classified as such at subsequent visits unless the patient develops additional symptoms warranting a re-classification to mixed phenotype. Missing data on prior visit will disqualify re-classification (participant must have data entered in the same measure to allow comparison and reclassification). The mixed phenotype is a persistent state, i.e, once a patient is classified as mixed phenotype at a given visit, then that patients remains mixed at all subsequent visits.

For those patients who initiated treatment with tafamidis after beginning participation in THAOS, phenotype treatment baseline will be the most recent phenotype classification prior to first dose.

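### As written, the phenotype rules leave ATTRv patients with a cardiac finding and only an already resolved ATTR-related neurologic or GI symptom Unclassified, and the off-label rule then counts their 80/61 mg use as off-label

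*SAP*

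**What the plan says.** All of the classification rules are in SAP Section 5.4. For symptomatic ATTRv patients:

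- **Predominantly cardiac** needs a qualifying cardiac finding (heart failure, dyspnea or a rhythm disturbance), together with "Absence of neurologic or gastrointestinal (GI) symptoms (ATTR unrelated, related or possibly symptoms) reported in medical history". Table 3 words the same condition as "No neuro or GI TTR related or possibly symptoms" and adds mPND below 1 or missing. The medical history form, per SAP Table 2, records "past and current signs, symptoms and medical diagnoses".
- **Predominantly neurologic** needs ongoing, ATTR-related neurologic or GI symptoms (or a qualifying mPND score) and none of those cardiac findings.
- **Mixed** needs a cardiac finding plus "Any ongoing neurologic or GI symptoms including erectile dysfunction, constipation, carpal tunnel syndrome of any severity, AND / OR" an mPND score of I or more. Table 3 also has ongoing in this row.
- **Unclassified** is the remainder: "Participants who do not qualify as predominately cardiac, neurologic, mixed phenotype or are asymptomatic".

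The off-label subgroup is "Patients not classified as predominantly cardiac or mixed phenotype at the first date of dosing with a dose of 80/61 milligram (mg) of tafamidis". SAP Section 2.2 gives its purpose: to identify patients who fall outside the ATTR-CM criteria.

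Two further statements bear on resolved symptoms. Under Changes of phenotype, an assigned phenotype is carried forward "Under the assumption that phenotype-related symptoms do not truly disappear, but are only possibly masked or temporarily resolved", and mixed is permanent. Under Predominantly Cardiac Phenotype, a sentence placed after the wild-type list says that neither cardiac nor neurologic symptoms have to be ongoing at a visit in order to count for phenotyping.

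**The concern.** The cardiac rule looks at the whole medical history, past symptoms included. The mixed rule looks only at what is ongoing. A resolved symptom can therefore bar a patient from cardiac without admitting the patient to mixed. The off-label subgroup takes everyone who is in neither class, so it absorbs these patients by default. Their Unclassified status does not show that they fail the ATTR-CM criteria, and they have a documented cardiac finding.

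Off-label use is a stated SAP objective with its own duration-of-treatment summary (Section 8.2.6, Exposure) and its own AE listing (Section 8.2.6, Adverse Events). The subgroup may be small, and Section 5.4 gives descriptive statistics only from 10 patients upward. A few patients assigned by default could decide whether it is summarized or only listed, and could change whom it describes. Section 8.2.4 plans a summary of past definitely and possibly related symptoms at enrollment, so such histories are an expected data category.

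**Working it through.** The plan states no figure to reproduce here, and all analyses are descriptive. The check is a walk through the rules.

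**Step 1: one patient, each rule.** Take a symptomatic ATTRv patient with heart failure, one ATTR-related carpal tunnel syndrome that resolved before first phenotyping, no ongoing neurologic or GI symptom, and mPND below I or missing.

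- Cardiac: fails. The history form holds past symptoms, and neither the text nor Table 3 permits a related one. The redacted bullet in this definition is joined by AND, so it can only narrow the class further.
- Neurologic: fails, because heart failure is present.
- Mixed: fails, because nothing is ongoing and the mPND route is not met.
- Asymptomatic: fails, because the patient is symptomatic.
- Result: Unclassified.

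**Step 2: vary the history and mPND.** Every row is symptomatic ATTRv with a qualifying cardiac finding and no earlier phenotype. I read the mPND entry of 1 in Table 3's mixed row as the text's I or more, and treat an ongoing symptom as sufficient for mixed, as the text does.

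| Neurologic/GI symptom | mPND | 5.4 text | Table 3 | If the sentence on ongoing status also covers ATTRv |
|---|---|---|---|---|
| None | below I or missing | cardiac | cardiac | cardiac |
| Resolved, related or possibly related | below I or missing | Unclassified | Unclassified | mixed |
| Resolved, unrelated | below I or missing | Unclassified | cardiac | mixed |
| Ongoing, related | below I or missing | mixed | mixed | mixed |
| Any of the above | I or more | mixed | mixed | mixed |

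For a resolved related symptom the gap occurs in two of the three mPND states (below I, missing), and text and table agree on it. For a resolved unrelated symptom text and table disagree.

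**Step 3: add carry-forward.** A patient classified cardiac or mixed at an earlier visit keeps that class, so the gap does not arise. A patient first classified neurologic, whose heart failure appears after the symptom has resolved, stays neurologic on a strict reading. That patient is not Unclassified but is still outside cardiac and mixed.

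**Step 4: effect on the off-label count.** At the first 80/61 mg dose,

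off-label count = N(neurologic) + N(asymptomatic) + N(Unclassified).

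N(Unclassified) cannot be negative, so including it can only raise the count. The documents give none of the three terms.

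**Step 5: effect on other outputs.** ECG and echocardiogram summaries in Section 8.2.6 are limited to cardiac or mixed phenotype at enrollment (plus neurologic-to-mixed switchers), so a patient Unclassified at enrollment is absent from the main groups there. Survival, hospitalization, AEs and deaths are reported by phenotype and overall. The patient leaves the cardiac and mixed strata but stays in the overall results.

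**The case against.** The strongest reply is the sentence saying that symptoms need not be ongoing to count. If it governs every phenotype, each resolved-symptom row above becomes mixed and nobody in those rows is off-label. This stands in part: the problem is then a conflict of wording. It does not remove the point, because the sentence follows the wild-type list, while the ATTRv mixed criterion and Table 3 both say ongoing. Two programmers could defend different off-label counts.

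A second reply is that the complement rule follows the wording of the objective and, for an AE listing, errs toward inclusion. That is fair, and it is why the fix drops nobody from the listing.

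Some stronger readings are tempting, and the documents do not support them:

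- *Every ATTRv patient with heart failure and a past related symptom is left without a phenotype.* Not so. mPND of I or more, another ongoing neurologic or GI symptom, or an earlier cardiac or mixed classification all prevent it.
- *The carry-forward assumption is flatly contradicted.* It justifies keeping a phenotype once assigned and sets no rule for first classification. There is tension with the ongoing requirement, but no direct contradiction.
- *These patients vanish from survival, hospitalization and safety results.* They remain in the overall sets. The off-label subgroup uses phenotype at first 80/61 mg dose and the ECG outputs use phenotype at enrollment, so the patients affected need not be the same.
- *Any unentered optional assessment makes a patient off-label.* Missing mPND alone does not block the cardiac class, and an assigned phenotype carries over visits without symptom data.

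**Conclusion.** The point holds in a narrow form. The patients concerned are symptomatic ATTRv patients with a qualifying cardiac finding, whose only related or possibly related neurologic or GI symptom had resolved by first phenotyping, with no other such symptom ongoing (related or not) and mPND below I or missing. The rules as written make them Unclassified, and the off-label definition then counts their 80/61 mg use as off-label, against the purpose in SAP Section 2.2. This assumes that the sentence on ongoing status applies to wild type only, as its position suggests; if it applies to ATTRv, the gap closes.

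The size cannot be derived. A reader might infer that off-label use is inflated several-fold, but any such multiple would rest on invented shares of Unclassified patients. Only the direction follows: a higher off-label count wherever such patients exist. The off-label preferred-term search in Section 8.2.6 does not use phenotype and is not affected.

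**What to change.** 1. In SAP Section 5.4 and the outputs that use the off-label subgroup, report separate lines. One holds patients classified predominantly neurologic or asymptomatic at the first 80/61 mg dose. The other holds Unclassified patients, labelled not determinable and split by qualifying cardiac finding present or data missing. Keep both in the AE listing with a flag, so that no safety data are lost. This changes no phenotype assignment.
2. Reconcile the cardiac, mixed and carry-forward text of Section 5.4 with Table 3 on whether a resolved neurologic or GI symptom counts for ATTRv phenotyping. State the scope of the sentence on ongoing status. Settle the resolved unrelated symptom, which the text bars from cardiac and Table 3 does not, and the patient first classed neurologic who later develops heart failure. Apply one rule before the final analysis. Which rule to adopt is for the sponsor to decide.

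The cost is SAP wording, one extra table split and a programming step on data already collected, with no change to care. Item 2 may reduce comparability with earlier THAOS phenotype counts; item 1 does not.

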**\*Changes of phenotype**

Under the assumption that phenotype-related symptoms do not truly disappear, but are only possibly masked or temporarily resolved, once determined, phenotype classification

PFIZER CONFIDENTIAL

will be carried forward to future visits even if there are no available symptom data at the subsequent visit. Patients classified as predominantly cardiac or predominantly neurologic at a given visit will continue to be classified as such at subsequent visits unless the patient develops additional symptoms warranting a re-classification to mixed phenotype. Missing data on prior visit will disqualify re-classification (participant must have data entered in the same measure to allow comparison and reclassification). The mixed phenotype is a persistent state, i.e, once a patient is classified as mixed phenotype at a given visit, then that patients remains mixed at all subsequent visits.

For those patients who initiated treatment with tafamidis after beginning participation in THAOS, phenotype treatment baseline will be the most recent phenotype classification prior to first dose.

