## 9.3. Variables

The objectives of THAOS are to describe the population of patients affected with ATTR amyloidosis and to enhance the understanding of the disease natural history, including the variability and progression of the hereditary and acquired forms of disease.

All visits are intended to be outpatient visits. Assessments are recommended but not required and will be determined by the investigator. All assessments that occur will be recorded in the THAOS electronic data record. The THAOS Electronic Case Report Form Completion Guidelines detail how the data for these assessments should be entered into the electronic data record. Blank worksheets and QoL questionnaires (available in patient’s native language) are available to download from the THAOS electronic data record.

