**Table 1 Summary of ongoing tafamidis safety concerns to be addressed in THAOS**

Level of Risk or Missing Information	Specific Concerns
Important potential risks	Hepatotoxicity Reproductive and developmental toxicity and lactation Changes in thyroid function, particularly in pregnant women
Important missing information	Safety and efficacy in patients with ATTR-PN variants other than Val30Met (B3461029 substudy) CCI █ Patients with severe hepatic impairment

Note: The important identified risks (Urinary tract infections, Diarrhea, Upper abdominal pain and Vaginal infections); important potential risks (Hypersensitivity reactions); and missing information (Safety and efficacy in elderly patients and Longer-term safety) have been removed from the list of ongoing safety concerns from the tafamidis EU Risk Management Plan (RMP) Update (v 9.3), approved on 17 February 2020 and therefore will not be addressed in the final clinical study report (CSR) for THAOS.

All AE/SAE data will be collected for patients treated with commercially available tafamidis; patients receiving tafamidis as part of their participation in an open-label clinical study will have AE/SAE data collection through the open-label clinical study; reporting of Health Events of Interest will be available for patients not treated with tafamidis.

All visits are intended to be outpatient visits. Table 2 presents the data collected throughout a patient's participation in THAOS per the case report form (CRF). All assessments listed in Table 2 are recommended, but not required and will be determined by the investigator.

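### SAP 5.4 blocks a change to mixed phenotype when the same measure is missing at the prior visit, which can delay or undercount conversions

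*SAP*

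**What the plan says.** The rule is in SAP 5.4, under changes of phenotype: "Missing data on prior visit will disqualify re-classification". A parenthesis gives the level at which it works: "participant must have data entered in the same measure to allow comparison and reclassification".

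Two other statements in that paragraph bear on it. A phenotype, once assigned, "will be carried forward to future visits even if there are no available symptom data at the subsequent visit". This rests on an assumption that "phenotype-related symptoms do not truly disappear, but are only possibly masked or temporarily resolved".

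Gaps in single measures are to be expected. SAP 2.1 says "All assessments listed in Table 2 are recommended, but not required and will be determined by the investigator", and Protocol 9.3 says "Assessments are recommended but not required and will be determined by the investigator". SAP Table 3 also accepts a predominantly cardiac classification with the mPND score missing.

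The resulting classification is used in three places:
- The converter subgroups in SAP 5.4, for example "Predominantly neurologic at baseline who become mixed phenotype post baseline", and the cardiac counterpart. Both are reported for post-baseline symptoms (SAP 8.2.4). The neurologic-to-mixed converters are also reported for ECG and baseline echocardiogram (SAP 8.2.6).
- The phenotype at treatment baseline for patients who start tafamidis after enrollment, which is the latest classification before first dose.
- The off-label subgroup in SAP 5.4: patients who are neither predominantly cardiac nor mixed when first given 80/61 mg.

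**The concern.** The SAP trusts an old observation enough to keep the phenotype through a gap, but not enough to compare a new finding with it. Take a predominantly neurologic patient with no qualifying cardiac finding at visit 1, the cardiac item not entered at visit 2, and heart failure recorded at visit 3. The patient meets the mixed definition at visit 3. The rule refuses the change because visit 2 is empty, although visit 1 holds a usable comparator.

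What happens at visit 4 is not stated. If the symptom must be new relative to visit 3, the conversion is lost. If visit 3 only has to contain data, the conversion is counted one visit late.

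Progression is a stated objective, so a converter count that depends on form completion is a poor measure of it. Off-label use is also an objective (SAP 2.2). A neurologic patient whose conversion is blocked before a first 80/61 mg dose is counted as off-label and enters the corresponding AE listing and exposure summary. Finally, subgroups need at least 10 patients for descriptive statistics, so undercounting can turn a converter table into a listing.

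**Working it through.** The documents give no conversion rate, per-visit missingness or expected number of converters, so there is no planned figure to reproduce.

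**Assumptions (none from the documents).** One relevant measure; 8 annual return visits after a complete baseline; conversion probability p = 0.08 per visit; the measure missing independently at each return visit with probability m = 10%, 20% or 30%; symptom persistent once present. Annual spacing follows SAP 2.1, and persistence follows the SAP 5.4 assumption quoted above.

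**Timing of conversion.** With T the visit of true conversion, P(T = t | T ≤ 8) = 0.08 × 0.92^(t−1) / (1 − 0.92^8). Since 0.92^8 = 0.513, the denominator is 0.487 and P(T = 1 | T ≤ 8) = 0.08 / 0.487 = 0.164.

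**Reading A: the symptom must be new against an observed immediately preceding visit.** Both visits t−1 and t must be observed. The probability is (1−m)² for t ≥ 2 and (1−m) for t = 1, because baseline is complete. Captured = (1−m)² + m(1−m) × 0.164.
- m = 10%: 0.81 + 0.09 × 0.164 = 0.82
- m = 20%: 0.64 + 0.16 × 0.164 = 0.67
- m = 30%: 0.49 + 0.21 × 0.164 = 0.52

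**Reading B: the preceding visit only needs data, so a blocked conversion counts at the next pair of consecutive observed visits.** Let a and b be the probabilities of being not yet counted with the current visit observed or missing. Start at visit t−1 with (1−m, m), or (1, 0) if t = 1. At each visit, new a = b(1−m) and new b = m(a+b). The share missed is a + b after visit 8, averaged over T.

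**Reading C: any earlier value of the measure serves.** Only an observation at or after t is needed. Captured = 1 − m^(9−t), averaged over T.

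| Missing per visit | A captured | B captured | C captured |
|---|---|---|---|
| 10% | 82% | 97% | 99% |
| 20% | 67% | 92% | 98% |
| 30% | 52% | 85% | 96% |

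At 30% missing, the losses are 48%, 15% and 4%. The 4% under C consists of conversions never observed again before follow-up ends, which no comparison rule can recover. The loss due to the rule itself is therefore about 48 − 4 = 44 points under A, 15 − 4 = 11 points under B, and nil under C.

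**Sensitivity at 30% missing with 5 return visits.** Losses are 46% (A), 24% (B) and 7% (C). Varying conversion from 2% to 20% per year gives 45–47%, 21–26% and 6–8%. With correlation 0.5 between missingness at successive visits, they are 38%, 23% and 14%.

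**Reporting threshold.** At 30% missing and 8 visits, an expected count of 10 needs 10/0.52 = 19.2, so 20 true converters, under A; 10/0.85 = 11.8, so 12, under B; and 10/0.96 = 10.4, so 11, under C.

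**The case against.** The strongest reply is that a reader might infer that a large share of conversions is never counted, and the documents do not support that. SAP 5.4 does not say that the symptom must be absent at the visit just before. It asks only for data in the same measure, and it says prior visit without saying immediately preceding. On that wording the example patient could become mixed at visit 4, one visit late. Under the most lenient reading the rule costs nothing. Permanent loss follows only from reading A. The references to developing additional symptoms and to comparison are compatible with A but do not settle it. This part of the objection stands.

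It also stands that no item-level missingness is given. The amendment log mentions a high drop-out rate, but as the reason for dropping a repeated-measures model, and dropout is not an intermittent gap. The calculation uses one measure, whereas an ATTRv patient can meet the neurologic side of the mixed definition through symptoms or through the mPND score, so a gap in one need not block the other. A difference in bias between treated and untreated sets is possible, but nothing in the documents shows it.

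The reach is limited too. Most visible summaries stratify by phenotype at enrollment, all analyses are descriptive (SAP 4), and the phenotype shift tables named in the amendment log cannot be assessed because nearby sections are redacted.

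Last, the rule has a proper purpose: a long-standing finding measured for the first time should not be counted as a conversion. That argues for a comparator, but not for ignoring one that was recorded before the gap.

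**Conclusion.** The point holds in limited form. The rule, combined with carry-forward and optional assessments, can delay or undercount conversions to mixed. It can also keep patients classed as neurologic at their first 61/80 mg dose, which adds them to the off-label subgroup.

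The size is uncertain for two reasons: the documents give no missingness in the relevant measures, and prior visit is undefined. Under the assumptions above with 30% missing, the same data could lose 48%, 15% or 4% of conversions depending on how the programmer reads one sentence. These figures show how far the readings diverge and do not predict what will happen in THAOS. The effect on the off-label count was not quantified.

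Protocol 9.9 says that methods for missing data would be described in the SAP. Here the SAP gives a rule but no count of blocked cases and no sensitivity analysis. The affected outputs are the converter subgroups, the phenotype at treatment baseline and the off-label subgroup. Summaries by phenotype at enrollment are untouched.

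**What to change.** Replace the sentence in SAP 5.4 with a rule that:
- compares each finding with the last non-missing value of the same measure at or after baseline;
- keeps the block only when no earlier value of that measure exists;
- states that a blocked conversion can be counted at a later visit.

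Report the number of patients blocked, by treated and untreated set.

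A symptom onset date, which SAP 8.2.4 already uses, may support the classification only where it is recorded and not imputed. SAP 7 sets a missing day to the 1st, and a missing day and month to 15 July, so an imputed onset can fall on the wrong side of a visit or of the first dose.

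The cost is a short SAP edit, one change in the derivation and one extra count. No new data are needed. The downside is that the visit of conversion is less exact after a gap: it is known only to lie between the last observed value and the visit at which the finding appears.
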